6.2.2.1 Composition

A Bexsero vaccine suspension for injection is supplied in pre-filled syringe.

Each 0.5 mL dose contains:

Recombinant N meningitidis group B NHBA fusion protein ^{1, 2, 3}	50 µg
Recombinant N meningitidis group B NadA protein ^{1, 2, 3}	50 µg
Recombinant N meningitidis group B fHbp fusion protein ^{1, 2, 3}	50 µg
Outer membrane vesicles from N meningitidis group B strain NZ98/254 measured as amount of total protein containing the PorA Pl.4 ²	25 µg

¹ Produced in *E coli* cells by recombinant DNA technology

² Adsorbed on aluminum hydroxide (0.5 mg Al3+)

³ NHBA (Neisseria Heparin Binding Antigen), NadA (Neisseria adhesin A), fHbp (factor H binding protein).

The vaccine contains the following excipients: sodium chloride, histidine, sucrose, water for injections.

6.2.2.2 Preparation and Administration

The procedures for administering Bexsero vaccine are the same as those described for the study product in [Section 6.1.1.2](#), with Bexsero vaccine to be given by IM injection in the contralateral arm (ie, the opposite to that which the MenACYW conjugate vaccine is administered).

Also see Bexsero vaccine package insert ([33](#)).

6.2.2.3 Dose Selection and Timing

All subjects in Group 4 will receive 1 dose of Bexsero vaccine on D0.

Note: A 2nd dose of Bexsero vaccine should be given at the D30 visit after completion of study procedures. The first dose of the vaccine will be provided by the Sponsor. Subsequent doses needed to complete the vaccination series will be procured by the sites and reimbursed by the Sponsor.

6.3 Product Logistics

6.3.1 Labeling and Packaging

The investigational product, MenACYW conjugate vaccine (single-dose vials), will be supplied with investigational labeling and packaging according to national regulations and will not be blinded. Each single dose of investigational product will be identified by a unique number on the detachable label and on the outer carton label. The carton label will also have a detachable label for the sites to attach to the source documents. See the Operating Guidelines for additional label details.

The concomitant products are not blinded and will retain original commercial labeling and packaging with no additional labels applied.

6.3.2 Product Shipment, Storage, and Accountability

6.3.2.1 Product Shipment

The Clinical Logistics Coordinator or designee will contact the Investigator or a designee to determine the dates and times of delivery of products.

Each vaccine shipment will include a temperature-monitoring device to verify maintenance of the cold chain during transit. On delivery of the product to the site, the person in charge of product receipt will follow the instructions given in the Operating Guidelines, including checking that the cold chain was maintained during shipment (ie, verification of the temperature recorders). If there is an indication that the cold chain was broken, this person should immediately quarantine the product, alert the Sanofi Pasteur representative, and request authorization from Sanofi Pasteur to use the product.

6.3.2.2 Product Storage

The Investigator will be personally responsible for product management or will designate a staff member to assume this responsibility.

At the site, products must be kept in a secure place with restricted access. Vaccines will be stored in a refrigerator at a temperature ranging from +2°C to +8°C. The vaccines must not be frozen. The temperature must be monitored and documented (see the Operating Guidelines) for the entire time that the vaccine is at the trial site. In case of accidental freezing or disruption of the cold chain, vaccines must not be administered and must be quarantined, and the Investigator or authorized designee should contact the Sanofi Pasteur representative for further instructions.

6.3.2.3 Product Accountability

The person in charge of product management at the site will maintain records of product delivery to the trial site, product inventory at the site, the dose(s) given to each subject, and the disposal of or return to the Sponsor of unused doses.

The necessary information on the product labels is to be entered into the source document and the CRF. If applicable, information may also be entered into the subject's vaccination card.

The Sponsor's monitoring staff will verify the trial site's product accountability records against the record of administered doses in the CRBs and the communication from the IRT (if applicable).

In case of any expected or potential shortage of product during the trial, the Investigator or an authorized designee should alert the Sanofi Pasteur representative as soon as possible, so that a shipment of extra doses can be arranged.

6.3.3 Replacement Doses

If a replacement dose is required (eg, because the syringe broke or particulate matter was observed in the syringe), the site personnel must either contact the IRT to receive the new dose allocation, or follow the instructions given in the Operating Guidelines.

6.3.4 Disposal of Unused Products

Unused or wasted products will be returned to the Sponsor in accordance with the instructions in the Operating Guidelines. Product accountability will be verified throughout the study period.

6.3.5 Recall of Products

If the Sponsor makes a decision to launch a retrieval procedure, the Investigator(s) will be informed of what needs to be done.

6.4 Blinding and Code-breaking Procedures

MET59 is an open-label study; therefore, there is no need for code-breaking procedures.

Until database lock and to prevent biases, the laboratory personnel performing the serology testing will be blinded to the group assignment. The laboratory will have a written procedure detailing how the blinding will be maintained.

6.5 Randomization and Allocation Procedures

MenACYW conjugate vaccine-primed subjects (from either MET50 or MET43) will be randomized in a 2:1:1 ratio to receive a booster dose of MenACYW conjugate vaccine alone (Group 1, 200 subjects) or to receive a booster dose of MenACYW conjugate vaccine concomitantly with licensed MenB vaccines (Trumenba vaccine; Group 3, 100 subjects, or Bexsero vaccine; Group 4, 100 subjects). Subjects primed with Menveo vaccine in MET50 or outside of Sanofi Pasteur trials will be assigned to Group 2 (200 subjects, which will not be randomized).

All subjects primed with MenACYW conjugate vaccine who meet the inclusion / exclusion criteria will be randomly assigned to Group 1, 3, or 4 in a 2:1:1 ratio, while subjects primed with Menveo vaccine will be automatically allocated to Group 2 (not randomized).

Site staff will call the IRT, enter identification and security information, and confirm a minimal amount of data in response to IRT prompts. The IRT will then state the vaccine dose assignment and whether the subject has been assigned to the D06 blood-draw subset. The full detailed procedures for randomization are described in the Operating Guidelines. If the subject is not eligible to participate in the trial, then the information will only be recorded on the subject recruitment log.

Subject numbers that are assigned by the IRT will consist of a 12-digit string (a 3-digit country identifier, a 4-digit study center identifier, and a 5-digit subject identifier). For example,

Subject 840000100005 is the fifth subject enrolled in Center Number 1 in the US (840 being the US country code).

Subject numbers should not be reassigned for any reason. The Research and Development (R&D) Site Quality Operations Department at Sanofi Pasteur will hold the randomization codes in a secured location.

6.6 Treatment Compliance

The following measures will ensure that the vaccine doses administered comply with those planned, and that any non-compliance is documented so that it can be accounted for in the data analyses:

- All vaccinations will be administered by qualified study personnel
- The person in charge of product management at the site will maintain accountability records of product delivery to the study site, product inventory at the site, dose(s) given to each subject, and the disposal of unused or wasted doses

6.7 Concomitant Medications and Other Therapies

At the time of enrollment, ongoing medications including but not limited to other therapies (eg, blood products), should be recorded in the source documents. All new medications prescribed for new medical conditions / AEs during study participation should also be recorded in the source documents.

Documentation in the CRB of concomitant medication(s) will be limited to specific categories of medication(s) (Categories 1, 2, and 3 as detailed below). Those will include Category 1, 2, and 3 medications ongoing at the time of inclusion in the study, or started at any time during the subject's participation in the trial. For category 3 medication, the period of reporting in CRB will be restricted to only 3 days (72 hours) prior to each blood sampling time point.

Collection period in source documents

Reportable medications (Category 1, 2, and 3) will be collected in the source documents from the day of first vaccination to the end of the trial.^a

Categories of Reportable medications and reporting period

Reportable medications include medications that impact or may impact the consistency of the safety information collected after any vaccination and/or the immune response to vaccination.

- 1) Category 1: Reportable medications with potential impact on the evaluation of the safety of the study vaccines. For example, antipyretics, analgesics, non-steroidal anti-inflammatory drugs (NSAIDs), systemic corticosteroids (therapy duration less than 2 weeks), and other immune modulators.

^a Subjects/ Subject's parents will be required to document all medications received in the Diary Cards. The sites will focus on only recording the medications belonging to the 3 categories in the other source documents.

Note: Topical steroids (Inhaled, otic, ophthalmic, nasal etc.) should not be captured or reported.

- Category 1 medications will be reported in the CRB from the day of first vaccination to the end of the solicited and unsolicited follow-up period after each vaccination. These medications will also be collected in the CRB for the 30- day period prior to the subsequent doses of the vaccine, wherever applicable (second, third, fourth, etc., in case of a multi-dose schedule with more than a 30-day interval between doses).

2) Category 2: Reportable medications with potential impact on immune response of the study vaccines and used to define the Per-Protocol Analysis Set (PPAS). For example:

- Influenza and other non-study vaccines: Influenza vaccine in the 2 weeks (14 days) preceding the trial vaccination up to the last blood draw and any other vaccines (other than the study vaccine) in the 4 weeks preceding the trial vaccination up to the last blood draw
- Immune globulins, blood or blood-derived products: used in the 3 months preceding the first blood draw and up to the last blood draw
- Immunosuppressive therapy such as immune-suppressors, immune-modulators with immunosuppressive properties, long-term systemic corticosteroids therapy (prednisone or equivalent for more than 2 consecutive weeks) within past 3 months, anti-cancer chemotherapy, anti-proliferative drugs such as DNA synthesis inhibitors, or radiation therapy: used in the 6 months preceding the first trial vaccination, and up to the last blood draw.
 - Category 2 medications will be reported in the CRB according to the collection period detailed above up to the last blood draw.

3) Category 3: Systemic (Oral or injectable) antibiotics, as they may interfere with bioassays used for antibody testing when taken before a blood draw.

- Category 3 medications will be reported in the CRB for the period of 3 days (72 hours) before each blood draw.

Note: Topical antibiotics (Inhaled, otic, ophthalmic, nasal, etc.) should not be captured or reported.

The information reported in the CRB for each reported medication will be limited to:

- Trade name
- Rationale for the origin of prescription: Whether it was a prophylactic^{a*} medication? Prophylactic medications will be recorded in the Action Taken section of the AE collection tables.
- Medication category (1, 2, or 3)
- Start and stop dates

^a Medication(s) prescribed for preventing AE occurrence (e.g. paracetamol to reduce the risk of fever)

Dosage and administration route, homeopathic medication, will not be recorded.

If the subject has received medications other than those listed in Categories 1, 2, and 3, the detailed information will be collected in the source documents only.

Medications given to treat an AE will be captured in the “Action Taken” section of the AE CRB only. No details will be recorded in the concomitant medication CRB unless the medication(s) received belongs to one of the prelisted categories.

7 Management of Samples

Blood samples for the assessment of antibody responses will be collected at D0, D06, and D30. See the [Tables of Study Procedures](#) and [Section 5.1.3](#) for details of the sampling schedule.

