- Whether the AE was related to the investigational product (for unsolicited systemic AEs)

The Investigator will assess the causal relationship between the AE and the investigational product as either “Not related” or “Related”, as described in [Section 9.3.2.7](#).

- Action taken for each AE (eg, medication)

The action(s) taken by the subject / parent or guardian to treat and/or manage any unsolicited AEs will be classified in the CRB using the following list (all applicable items should be checked):

- None
- Medication
- Health care provider contact
- Hospitalized
- Discontinuation of study vaccination
- Whether the AE was serious

For each SAE, the Investigator will complete all seriousness criteria that apply (outcome, elapsed time, and relationship to study procedures)

- Whether the AE caused study discontinuation

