4.4.2.5.2 Action Taken

This information will be summarized as collected, including missing observations. No derivation or imputation will be done.

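### Protocol 6.7 records preventive medication under Action Taken, a field defined elsewhere as treatment or management of an event, so the Medication category of the action-taken summaries can be inflated by an unknown amount, possibly zero.

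*Protocol*

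**What the plan says.** Protocol 6.7 lists what the case report book holds for each reportable medication. One item asks about prophylaxis ("Rationale for the origin of prescription: Whether it was a prophylactic"), and the same item then says "Prophylactic medications will be recorded in the Action Taken section of the AE collection tables". A footnote defines the term: "Medication(s) prescribed for preventing AE occurrence (e.g. paracetamol to reduce the risk of fever". Further down, the section says of therapeutic drugs: "Medications given to treat an AE will be captured in the “Action Taken” section of the AE CRB only". It adds that such drugs also get a concomitant medication entry if they belong to a listed category. Antipyretics, analgesics and NSAIDs are Category 1, and "Category 1 medications will be reported in the CRB from the day of first vaccination" until the end of solicited and unsolicited follow-up.

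Protocol 9.3.2.3.3 describes the field differently: "The action(s) taken by the subject / parent or guardian to treat and/or manage any unsolicited AEs will be classified in the CRB". Section 9.3.2.3.2 says the same for solicited reactions. Both give five options: none, medication, health care provider contact, hospitalized, and discontinuation of study vaccination. None of them denotes prophylaxis.

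Action taken is an attribute of observational safety endpoints 2, 3 and 4 (Protocol 9.3.2.2) and is listed for solicited reactions and unsolicited events in SAP Table 5.2. On handling, SAP 4.4.2.5.2 says "This information will be summarized as collected, including missing observations" and rules out any derivation.

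**The concern.** A preventive dose precedes the event and does not treat it, so one field is given two incompatible meanings. Treatment and prevention share one *Medication* code, and nothing on the adverse event record tells them apart. A reaction that followed a preventive antipyretic and needed no treatment belongs under *None*. Under 6.7 it can appear as *Medication*.

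What is at stake is how the action-taken tables are read. The share of reactions needing medication is a natural summary of how troublesome reactogenicity was. If the category mixes treatment with prevention, a reader of the study report cannot tell. Enrollment of 200 subjects each in Groups 1 and 2 is justified by the booster safety database, so these tables have readers.

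The rule also cannot be carried out when a subject takes prophylaxis and no event follows, because no adverse event record exists to hold the dose. With up to 40 sites, recording practice may then vary.

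**Working it through.** The plan states no figure on this point, so there is nothing to reproduce. The check sets the passages side by side and then illustrates scale.

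**Text**

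1. Protocol 6.7: prophylaxis means prevention of an event, and it is recorded under Action Taken.
2. Protocol 6.7: medication given to treat an event is recorded in the same place.
3. Protocol 9.3.2.3.2 and 9.3.2.3.3: the field covers treatment or management only, with a single medication code.
4. SAP 4.4.2.5.2: tabulated as collected, with no derivation.
5. SAP 4.4.3.5: rules on restricted medication concern Categories 2 and 3 only, so Category 1 antipyretics are not picked up there.
6. Protocol 6.7: the concomitant medication record carries the prophylactic indicator and start and stop dates. No SAP section uses them for action taken.

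Item 1 contradicts item 3. Items 2 and 4 mean that the field and its planned analysis do not resolve the contradiction. Item 6 means that part of the information needed to do so is collected.

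**When a miscount occurs.** Four things must coincide: the subject took prophylaxis; a reaction followed; the dose was entered against that reaction; and no medication was given to treat it. If no event follows, the contribution is zero.

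**Scale, on assumed values.** Let m be the share of reactions truly treated with medication, and q the share of the remaining reactions that carry only a preventive dose entry. Then

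reported share = m + q(1 − m), excess = q(1 − m).

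Example: m = 30%, q = 10% gives 0.30 + 0.10 × 0.70 = 0.37, an excess of 7.0 percentage points.

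| m | q = 0 | q = 2% | q = 5% | q = 10% | q = 20% |
|---|---|---|---|---|---|
| 10% | 10.0% | 11.8% | 14.5% | 19.0% | 28.0% |
| 30% | 30.0% | 31.4% | 33.5% | 37.0% | 44.0% |
| 50% | 50.0% | 51.0% | 52.5% | 55.0% | 60.0% |

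The documents give neither m nor q. The grid shows how the excess behaves and estimates nothing for this trial.

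**Reach.** Solicited reaction presence, intensity, onset and days of occurrence are derived from daily records (SAP 4.4.2.1). Medically-attended events are derived from the health care provider contact option (SAP 4.4.2.4). The primary test uses titers. None of these reads the *Medication* entry.

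**The case against.** The strongest reply is that this is a wording slip in one attribute of descriptive endpoints for which no hypothesis is tested. The diary card asks for the action taken for each event, which ties entries to events. Prophylaxis is flagged and dated in the medication record, and a Category 1 dose with no later reaction is still captured there. The footnote speaks of prescribed medication, which may be narrower than any preventive dose taken. No passage says that a preventive dose is to be counted as treatment.

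Most of this stands, and it limits the point. It does not remove the contradiction, because a site cannot satisfy 6.7 and 9.3.2.3 together. Nor do the flag and dates help while the SAP plans no use of them and excludes derivation.

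Two stronger readings are tempting. A reader might infer that preventive antipyretics are in fact counted as treatment and that the action-taken results are overstated. The documents do not support this, because they give no rate for any of the four conditions. A reader might also infer that, in an open-label trial, prophylaxis differs between booster alone and co-administration and so biases Group 1 against Groups 3 and 4. Differential use is conjecture, and the plan only summarizes action taken by group.

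**Conclusion.** The conflict between Protocol 6.7 and Protocol 9.3.2.3.2 and 9.3.2.3.3 is real, and the SAP carries it into the tables unchanged. The conclusion is that the *Medication* category can be inflated. That it is inflated has not been shown. The size cannot be determined from the documents and includes zero. The effect is confined to one descriptive item of observational safety endpoints 2 to 4. This assumes that sites follow 6.7 literally and that some subjects take prophylaxis, then have a reaction they do not medicate. It is worth correcting because the correction is cheap and the resulting label is otherwise ambiguous.

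**What to change.** **Recording.** Reconcile the passages. State in 6.7 and in the CRF completion instructions that prophylactic medication goes in the concomitant medication record under its existing indicator and not under Action Taken, which is limited to medication given to treat or manage the event. This changes where data are recorded and no clinical rule.

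**Data already collected.** Planned inclusion ended on 02 March 2020 (Protocol 5.1.5), so the last planned D0 to D07 window closed on 09 March. Protocol version 6.0 is dated 06 April 2020. On that calendar, rewording alone would not alter endpoints 2 and 3. SAP 4.4.2.5.2 should therefore be amended so that a *Medication* entry is not counted as treatment, or is shown on a separate line, only where the sole supporting medication record is flagged prophylactic and started before the reaction's onset. Entries with any treatment medication after onset stay. Simply deleting flagged entries would remove true treatment in subjects who took both.

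**Cost.** One sentence in 6.7, one CRF instruction, one SAP derivation, and data-review effort to match medication records to events, since no direct link is documented. Two limits favor the separate line. Only dates are recorded, so same-day order may be unclear. A treatment drug outside the listed categories has no concomitant medication entry, so its absence does not prove that no treatment was given.

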7.1 Sample Collection

At the D0, D06 and D30 visits, 20 mL of blood will be collected in tubes provided by or recommended by the Sponsor. Immediately prior to the blood draw, the staff member performing the procedure will verify the subject’s identity as well as the assigned subject’s number and sampling stage on the pre-printed label, and will attach the label to the tube. When vaccination and blood sample collection occur at the same visit and vaccine is given only in one of the arms, blood is to be taken from the limb opposite to the one that will be used for vaccination, if possible.

7.2 Sample Preparation

Detailed instructions on how to prepare blood samples for assessment of antibody response are contained in the Operating Guidelines provided to the site. An overview of the procedures is provided here.

Following the blood draw, the tubes are to be left undisturbed, positioned vertically and not shaken, for a minimum of 1 hour and a maximum of 24 hours in order to allow the blood to clot. Samples can be stored at room temperature for up to 2 hours; beyond 2 hours, they must be refrigerated at a temperature of +2°C to +8°C after the period of clotting at room temperature and must be centrifuged within a maximum of 24 hours.

The samples are then centrifuged, and the serum is transferred to the appropriate number of aliquoting tubes. These tubes are pre-labeled with adhesive labels that identify the study code, the subject’s number and the sampling site or visit number.

The subject’s number and the date of sampling, the number of aliquots obtained, the date and time of preparation, and the subject’s consent for future use of his / her samples are to be specified on a sample identification list and recorded in the source document. Space is provided on this list for comments on the quality of samples.

